8.3. Secondary Endpoint

Histological liver biopsy results (obtained in the initial study) versus clinical outcome at time of current data collection. .

8.4. Safety Endpoints

There are no safety endpoints in this trial since it is retrospective and observational only.

8.5. Sample size

This protocol is looking back on retrospective data from Exalenz clinical studies HIS-EX-408 and/or PLT-BID-1108 . In the initial studies there were 414 and 165 subjects enrolled respectively, thus this retrospective study may include up to 579 subjects.

| | |
|--|--|
| Exalenz Bioscience Ltd. | Last update on: April 01, 2015 |
| Protocol: The predictive value of the BreathID, ¹³ C-Methacetin breath test for Hepatic Decompensation; a retrospective analysis | Version Level: 1b |
| Document No.: CSD00074 | Page 16 of 23 |

8.6. Statistical Analyses

All statistical analyses and data presentations, including tabulations and listings, will be performed using the SAS version 9.3 (or higher) software. Statistical tests will be two-sided and the level of significance is 0.05. Nominal p-values will be presented.

Baseline demographics and medical characteristics will be presented in tabular format. The statistical evaluation of baseline characteristics will include all available data.

For continuous variables, the following descriptive statistics will be given: N, Mean, Standard Deviation, Minimum, Median and Maximum values; for discrete variables, the Frequency and Percentage of patients or events will be provided.

For comparison of means (continuous variables), the two-sample t-test or the Wilcoxon rank sum test will be used as appropriate. For comparison of proportions (categorical variables), the Chi-squared test or Fisher's exact test will be used as appropriate.

Kaplan-Meier curves of the time event data will be presented. For comparison of time to event data, the log rank test will be used. Cox regression will be used to estimate hazard ratios, their level of significance and 95% confidence limits.

Risk stratification may be performed by categorizing the MBT into risk groups, for these groups Kaplan-Meier Curves of the time to clinical outcome will be presented for the MBT categories as well as the liver biopsy results to compare predictive value.

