5. Newly diagnosed varices or variceal bleeding
6. SBP (spontaneous bacterial peritonitis)/Sepsis
7. HRS (Hepatorenal syndrome)
8. HCC (hepatocellular carcinoma)
9. Increase in CTP (Child Turcotte Pugh) Score by 3 points
10. Increase in MELD score by 5 points

Primary Endpoints:

Time to the first occurrence of a hepatic decompensation event (as defined in the primary outcome measures).

Secondary endpoints:

| | |
|--|--|
| Exalenz Bioscience Ltd. | Last update on: April 01, 2015 |
| Protocol: The predictive value of the BreathID, ¹³ C-Methacetin breath test for Hepatic Decompensation; a retrospective analysis | Version Level: 1b |
| Document No.: CSD00074 | Page 5 of 23 |

- Histological liver biopsy results (obtained in the initial study) versus clinical outcome at time of current data collection
- Time to each of the individual events as follows:
 1. Death (liver related)
 2. Transplantation (cadaveric and living donors)
 3. Ascites
 4. HE (Hepatic Encephalopathy)
 5. Newly diagnosed varices or variceal bleeding
 6. SBP (spontaneous bacterial peritonitis)/Sepsis
 7. HRS (Hepatorenal syndrome)
 8. HCC (hepatocellular carcinoma)
 9. Increase in CTP (Child Turcotte Pugh) Score by 3 points.
 10. Increase in MELD score by 5 points

Study Design: Retrospective, multicenter clinical evaluation of patients' outcome initially enrolled (n=414+165=579) into the Exalenz pivotal studies (protocols HIS-EX-408 and/or PLT-BID-1108 respectively). The information collected in this study will be anonymous.

Study Population: A maximum of 579 adult male or female patients enrolled into the Exalenz studies (protocols HIS-EX-408 and/or PLT-BID-1108) who performed a ¹³C-Methacetin Breath Test.

Main Inclusion Criteria: Patient has been tested with the MBT in the past Exalenz pivotal studies protocols HIS-EX-408 and/or PLT-BID-1108 (from August 2008 to September 2012).

Main Exclusion Criteria: Patient had been enrolled into the pivotal study but not included in the final analysis due to conditions / factors interfering with the MBT (i.e. exclusion criteria within the HIS-EX-408 and/or PLT-BID-1108 study).

Statistical Analysis:

Introduction:

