It is anticipated that 3-5% of patients with stable cirrhosis will develop hepatic decompensation and achieve an end-point within a year. An additional 1-2% would be expected to die from these complications per year. This study is conducted 6 years post initial enrollment, accordingly the expected amount of complications are expected to be 6 times higher. Furthermore some of the patients that were not considered as cirrhotic at the time of enrollment may progress to cirrhosis and deteriorate.

| | |
|--|--|
| Exalenz Bioscience Ltd. | Last update on: April 01, 2015 |
| Protocol: The predictive value of the BreathID, ¹³ C-Methacetin breath test for Hepatic Decompensation; a retrospective analysis | Version Level: 1b |
| Document No.: CSD00074 | Page 6 of 23 |

All patients with valid breath test results from the HIS-EX-408 and/or PLT-BID-1108 trials will be candidates for this follow up trial.

Analyses:

All statistical analyses and data presentations, including tabulations and listings, will be performed using the SAS version 9.3 (or higher) software. Statistical tests will be two-sided and the level of significance is 0.05. Nominal p-values will be presented.

The ability of MBT to predict morbidity and mortality and other complications will be evaluated using survival analysis methods, mainly Kaplan-Meier curves and Cox regression analyses.

| | |
|--|--|
| Exalenz Bioscience Ltd. | Last update on: April 01, 2015 |
| Protocol: The predictive value of the BreathID, ¹³ C-Methacetin breath test for Hepatic Decompensation; a retrospective analysis | Version Level: 1b |
| Document No.: CSD00074 | Page 7 of 23 |

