2. OBJECTIVES

The objectives of this study are:

- To evaluate the ability of the Methacetin Breath Test to detect hepatic decompensation events
- To evaluate the relationship between liver Biopsy and clinical outcome and show that the MBT has a better predictive ability of clinical outcome than liver biopsy.

| | |
|--|--|
| Exalenz Bioscience Ltd. | Last update on: April 01, 2015 |
| Protocol: The predictive value of the BreathID, ¹³ C-Methacetin breath test for Hepatic Decompensation; a retrospective analysis | Version Level: 1b |
| Document No.: CSD00074 | Page 12 of 23 |

- To evaluate the ability of the MBT to predict each of the individual liver related complications.

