3. ENDPOINTS

3.1. Primary Efficacy Endpoints

The MBT results and the time to hepatic decompensation events:

Hepatic decompensation is defined as the occurrence of at least one of the following events in the time frame between the last ¹³C-Methacetin Breath Test (MBT) to the time of data collection:

1. Death (liver related)
2. Transplantation (cadaveric and living donors)
3. Ascites
4. HE (Hepatic Encephalopathy)
5. Newly diagnosed varices or variceal bleeding
6. SBP (spontaneous bacterial peritonitis)/Sepsis
7. HRS (Hepatorenal syndrome)
8. HCC (hepatocellular carcinoma)
9. Increase in CTP (Child Turcotte Pugh) Score by 3 points
10. Increase in MELD score by 5 points

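### Section 8.6 plans Kaplan-Meier curves without a rule for competing death or transplantation; if these are censored, the absolute risk of a single event reads somewhat too high

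*Combined protocol and SAP*

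**What the plan says.** Section 8.6 (Statistical Analyses) plans three tools for time-to-event data. For display, "Kaplan-Meier curves of the time event data will be presented". Groups are compared by the log-rank test. For effect size, "Cox regression will be used to estimate hazard ratios, their level of significance and 95% confidence limits". Curves by MBT risk group and by biopsy result may also be shown, to compare predictive value.

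The endpoints to which these tools apply are:

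- **Primary composite (sections 3.1 and 8.2).** Time to the first of ten events. Transplantation is one of them. Death counts only if it is liver related.
- **Single events (section 3.2 and the Synopsis).** Time to each of the ten events separately. Section 2 gives this its own objective: "To evaluate the ability of the MBT to predict each of the individual liver related complications".

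No section gives a censoring rule, a competing-event rule or a cumulative-incidence method. Section 6.5, on completion and withdrawal, is marked as not applicable. Section 6.3 asks for hepatic complication events to be recorded and does not name non-liver death.

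**The concern.** A patient who dies or is transplanted before developing, say, ascites or HCC either cannot have that event any more or is no longer at the same risk of it. Two treatments of such a patient are possible, and the plan does not choose between them:

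- **Censor at the date of death or transplantation.** 1 minus Kaplan-Meier then estimates the risk in a setting where the competing event does not happen. Read as the chance that a patient will have the event, it is too high.
- **Keep the patient at risk, event-free, until data collection.** The same curve then approximates cumulative incidence.

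A reader of the report could not tell which of the two a curve shows. The stake is the absolute risk read from the curves, mainly for single events. The background in section 1.1 itself describes patients with cirrhosis who die before they can be considered for or receive a transplant, so competition between these events is part of the plan's own picture of the disease.

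**Working it through.** **Inputs from the document**

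- Any decompensation: "It is anticipated that 3-5% of patients with stable cirrhosis will develop hepatic decompensation" per year (Synopsis, Statistical Analysis).
- Death: "An additional 1-2% would be expected to die from these complications per year" (same place).
- Horizon: "This study is conducted 6 years post initial enrollment" (same place), so T = 6.
- Test dates: "from August 2008 to September 2012" (Synopsis, Main Inclusion Criteria). Follow-up to the protocol date of 1 April 2015 is 6.66 years from 1 August 2008 and 2.58 years from 1 September 2012.

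**Inputs that are assumed.** The document gives no rate for any single event, for transplantation or for non-liver death. A single-event rate of 1-3% per year and a non-liver death rate of 0.5-1% per year are used for illustration. Rates are taken as constant and independent.

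**The plan's own figures.** The document states no single-event or competing-risk figure to reproduce. Its statement that complications will be 6 times higher gives 6 x 3% = 18% to 6 x 5% = 30%. With constant rates the same inputs give 1 - exp(-0.18) = 16.5% to 1 - exp(-0.30) = 25.9%.

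**Formulas.** With event rate h and competing rate c:

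- Kaplan-Meier risk, competing events censored: 1 - exp(-hT)
- Cumulative incidence: h/(h+c) x [1 - exp(-(h+c)T)]

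Worked case, h = 0.03, c = 0.02, T = 6: 1 - exp(-0.18) = 16.47%; 0.6 x [1 - exp(-0.30)] = 0.6 x 25.92% = 15.55%; excess 0.92 points.

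**Results** (differences taken before rounding)

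| Case | T (years) | h per year | c per year | 1 - KM | Cumulative incidence | Excess (points) |
|---|---|---|---|---|---|---|
| Single event | 6 | 1% | 1% | 5.82% | 5.65% | 0.17 |
| Single event | 6 | 1% | 2% | 5.82% | 5.49% | 0.33 |
| Single event | 6 | 3% | 1% | 16.47% | 16.00% | 0.47 |
| Single event | 6 | 3% | 2% | 16.47% | 15.55% | 0.92 |
| Plan's any-event upper rate | 6 | 5% | 2% | 25.92% | 24.50% | 1.42 |
| Short follow-up | 2.58 | 3% | 2% | 7.45% | 7.26% | 0.19 |
| Larger competing rate | 6 | 3% | 5% | 16.47% | 14.30% | 2.18 |
| Larger competing rate | 6 | 3% | 7% | 16.47% | 13.54% | 2.94 |
| Composite, non-liver death competing | 6 | 3% | 0.5% | 16.47% | 16.24% | 0.24 |
| Composite, non-liver death competing | 6 | 5% | 1% | 25.92% | 25.19% | 0.72 |

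The excess keeps growing as c grows, and c is not known from the document once transplantation and non-liver death are included.

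**Which deaths compete.** The plan's 1-2% are deaths from complications. A death that follows the single event under study does not compete with it, so using the whole 1-2% may overstate c from that source. Transplantation and non-liver death, which are not in that rate, work the other way.

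**Tests and hazard ratios.** With competing events censored at their date, the log-rank test and Cox model compare and estimate cause-specific hazards. They are valid as such and are not inflated. Section 8.6 only lacks the label.

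**The case against.** The strongest reply is that little depends on this.

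- No absolute risk at a fixed time is an endpoint, and the stated purpose of the risk-group curves is to compare predictive value. The document does not show whether the excess differs between MBT groups. This stands, and it keeps the point minor.
- Curves for each single event are inferred from section 8.6 read with section 3.2; section 8.3 lists only the biopsy endpoint. This also stands, although section 2 and section 3.2 make the single events an objective and an endpoint, and section 8.6 names no other display for such data.
- The excess is below the precision of the curves. With all 579 patients and no censoring, a risk of 16.5% has a 95% interval of about 1.96 x sqrt(0.165 x 0.835/579) = 3.0 points either way. That is correct. The excess is nevertheless a bias of known direction that more patients would not remove, and it costs little to avoid.
- Non-liver death may be collected anyway: the CRF is not among the documents, and classifying a death as liver related already requires its cause. This is fair. The claim is only that section 6.3 does not name it.

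Two stronger readings may tempt a reader. The first is that the hazard ratios or p-values are biased; they are not, for the reason given above. The second is that the excess can be capped, for example near 2.2 points. Such a cap needs upper limits on the single-event, transplantation and non-liver death rates that the document does not give, and it also needs constant rates.

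**Conclusion.** The omission is real and the direction is certain: if competing events are censored, 1 minus Kaplan-Meier overstates the absolute risk of a single event. The sizes above illustrate the effect and are not estimates for this cohort. The 0.2 to 0.9 point range rests on the assumed 1-3% per year single-event rate as well as the plan's death rate. The 1.4 point figure uses the plan's upper rate for any event, which is more than a single event would be expected to reach. Beyond that, the document supports no upper limit.

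The plan's rates are for stable cirrhosis, while the cohort also includes patients not considered cirrhotic at enrollment, so actual rates may differ. Six years is also near the longest follow-up, and most shorter follow-up times would give a smaller excess.

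It should not be inferred that the primary endpoint is seriously affected. Liver-related death and transplantation are already components of the composite, so only non-liver death competes with it. Nor is there any excess if patients are in fact kept at risk to data collection. Severity is minor.

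**What to change.** In section 8.6:

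- For each single event, present the Aalen-Johansen cumulative incidence instead of 1 minus Kaplan-Meier. Treat transplantation, and any death not counted as that event, as competing events. Transplantation does not compete for its own endpoint.
- For the composite, do the same with non-liver death as the competing event.
- Keep the log-rank test and Cox regression with competing events censored at their date, and label the results cause-specific.

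In section 6.3, add the date and cause of every death, including non-liver death. This is best settled before data collection, because a cause of death that was not abstracted cannot be recovered at the analysis stage.

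The cost is a few sentences, slightly more analysis, and one item abstracted from files that are already under review. Reported risks may be slightly lower if competing events would otherwise have been censored.

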4. STUDY DESIGN

This is a retrospective, multi-center, non-randomized, open label study of the ¹³C-Methacetin BreathID Test (MBT) that will include all patients previously enrolled into the BreathID pivotal study (HIS-EX-408) and/or the PLT-BID-1108 study, that have performed a valid MBT. The information collected in this study will be anonymous.

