5. STUDY POPULATION

All subjects previously enrolled into the BreathID pivotal study (HIS-EX-408) and/or the PLT-BID-1108 study and had a valid ¹³C-Methacetin breath test result with or without a valid liver biopsy result at the time of MBT will be included in this retrospective investigation.

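### Section 8.6 pools two source studies (414 + 165 patients) with no study stratum or by-study result, so a between-study contribution to the MBT hazard ratio, if there is one, would go unseen

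*Combined protocol and SAP*

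**What the plan says.** The population comes from two earlier studies. The synopsis describes patients "initially enrolled (n=414+165=579) into the Exalenz pivotal studies (protocols HIS-EX-408 and/or PLT-BID-1108 respectively". Section 4 describes a study "that will include all patients previously enrolled into the BreathID pivotal study (HIS-EX-408) and/or the PLT-BID-1108 study, that have performed a valid MBT", section 5 defines the population in the same way ("All subjects previously enrolled into the BreathID pivotal study (HIS-EX-408) and/or the PLT-BID-1108 study"), and section 8.5 adds the two enrolments: "In the initial studies there were 414 and 165 subjects enrolled respectively, thus this retrospective study may include up to 579 subjects".

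Section 8.6 plans Kaplan-Meier curves and two inferential tools for the time-to-event outcome: "For comparison of time to event data, the log rank test will be used" and "Cox regression will be used to estimate hazard ratios, their level of significance and 95% confidence limits". The only stratification it mentions is an optional grouping by MBT category. Its two-sample tests for means and proportions do not name the groups to be compared, so they do not commit the sponsor to comparing the source studies. No section names a source-study stratum, covariate, interaction or by-study estimate.

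On case mix, the statistical introduction in the synopsis says that "some of the patients that were not considered as cirrhotic at the time of enrollment may progress to cirrhosis and deteriorate". It gives one event rate, for stable cirrhosis only: "It is anticipated that 3-5% of patients with stable cirrhosis will develop hepatic decompensation and achieve an end-point within a year". Neither statement is split by source study.

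**The concern.** A pooled, unstratified Cox model compares each patient who has an event with everyone still at risk, from either study. Some of those comparisons are between studies. If patients of one study had both worse MBT and more events for reasons that the MBT does not measure, part of the pooled hazard ratio reflects which study a patient came from. If the study with worse MBT had fewer events at the same MBT, pooling hides real prediction.

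Both differences are needed for material confounding. A difference in MBT alone, in hazard alone, in length of follow-up alone, or in severity that the MBT itself captures does not produce it. The plan contains no result that would tell these cases apart.

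The main objective in section 8.1 is whether the MBT predicts time to decompensation, and section 1.10 expects a validated claim to influence clinical practice. A reader will want to know whether the test ranks risk among patients of the same study, or only across the combined set.

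**Working it through.** **Plan's own figure.** 414 + 165 = 579, as in section 8.5. Shares: 414/579 = 71.5% and 165/579 = 28.5%. The plan states no power, event target or design hazard ratio, so there is nothing further to reproduce.

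**Inputs from the documents.** Study sizes as above; two-sided 0.05 (8.6); 3-5% per year in stable cirrhosis and 6 years since enrolment (synopsis); MBT dates August 2008 to September 2012 (synopsis); protocol date April 2015.

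**Assumptions, because the documents are silent.** MBT is on a continuous scale, with effects per within-study SD; section 8.6 does not say whether the predictor is PDR, CPDR or the Hepatic Impairment Score. PLT-BID-1108 is taken as the study with worse MBT, by *d* SD, and its hazard at the same MBT is *h* times that of HIS-EX-408. There are two event scenarios:
- A: 4% per year in HIS-EX-408 with 6 years of follow-up. This is probably high, because the rate is for cirrhosis.
- B: 2% per year, with follow-up uniform over 2.5 to 6.7 years.

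**Step 1: approximate size of the shift.** By the omitted-variable formula, the pooled log hazard ratio per SD moves by about

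log(*h*) × *w*·*d* / (1 + *w*·*d*²), with *w* = 0.715 × 0.285 = 0.204.

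- *d* = 0.5, *h* = 2: 0.693 × 0.1019/1.051 = 0.067, a factor of 1.07. A true 1.30 becomes 1.30 × 1.07 = 1.39. With *h* = 0.5 it becomes 1.30/1.07 = 1.22 (1.215 before rounding).
- *d* = 0.25, *h* = 1.5: 0.405 × 0.0509/1.013 = 0.020, a factor of 1.02.

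**Step 2: approximate false-positive rate with no within-study effect, at *d* = 0.5, *h* = 2.** The standard error is about 1/√(events × 1.051).
- A: events are 414(1 − e^−0.24) + 165(1 − e^−0.48) = 88 + 63 = 151. SE = 0.079, shift/SE = 0.85, two-sided rejection about 14%.
- B: the same calculation, averaged over follow-up, gives 36 + 28 = 64 events. SE = 0.122, shift/SE = 0.55, rejection about 9%.

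**Step 3: simulation of the Cox models.** Several independent runs of 1,500 to 6,000 simulated trials at 414 + 165 agree with these approximations. Ranges are across runs.

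| Case | Pooled | Stratified |
|---|---|---|
| No effect, 0.5 SD, ×2: rejection, A | 14.7-16.0% | 4.6-5.3% |
| No effect, 0.5 SD, ×2: rejection, B | 9.4-10.3% | 4.6-5.8% |
| No effect, 0.25 SD, ×1.5: rejection, A and B | 5.4-6.3% | 4.6-5.3% |
| No effect, one difference only: rejection | 4.9-5.0% | about 5% |
| True HR 1.30, 0.5 SD, ×2: HR | 1.39-1.41 | 1.30-1.31 |
| True HR 1.30, 0.5 SD, ×0.5: HR | 1.22-1.23 | 1.30-1.31 |

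**Step 4: cases without bias.** If hazard depends on MBT alone (HR 1.5, gap 1 SD), pooled and stratified both give 1.50. If the studies differ in MBT and in follow-up length but share the same hazard at the same MBT, both models reject a true null in 5.5% of trials, and both give 1.30 when 1.30 is true.

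**The case against.** The strongest reply is that nothing in the documents says the studies differ. The synopsis background describes both together, as studies of the MBT in chronic liver patients with one stated aim, and the remark about non-cirrhotic patients concerns the whole population. This stands. The bias is a possibility that the plan leaves unchecked, and its size and direction are unknown.

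Second, the stated objective is prediction in patients with chronic liver disease, not prediction independent of source study. This also stands. A reader might infer that pooling makes the primary hazard ratio invalid. The documents do not support that: it is a valid description of how the MBT orders risk in the combined patients.

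Third, the effect may not matter if the test is strong. Section 1.10 cites a hazard ratio of up to 12 from previous company studies, on an unstated scale. At an assumed 2.0 per SD with a 0.5 SD gap, the pooled estimate is 2.13-2.16 or 1.86-1.88 (for a two-fold difference one way or the other) and power is at least 99.6%. The conclusion would not change, although coverage of the pooled 95% interval for the within-study value falls to about 84-92%.

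Fourth, by-study estimates and an interaction test would be weak. PLT-BID-1108 might contribute anywhere from about 9 to about 71 events under the assumptions used, and an interaction (HR 1.3 in one study, 1.0 in the other) would be detected in only 14-36% of trials. This is a good reason to keep the addition small.

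Finally, source study is only one possible confounder, and the unnamed MBT variable is a larger gap. Both are true. But source study is known for every patient and is built into how the population was formed, so adjusting for it costs little.

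**Conclusion.** The omission is real and worth correcting, as an inexpensive improvement and not as the repair of an error. No figure in the plan is wrong on this point.

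The size depends on unverified assumptions. At a 0.5 SD gap and a two-fold hazard difference, 1.30 becomes about 1.40 or 1.22, and a true null is rejected in about 10% to 16% of trials. At 0.25 SD and 1.5-fold there is almost no inflation. If only one difference is present, the null rejection rate stays at 5%.

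Much larger figures can be produced. With a binary MBT that is low in 20% of one study and 60% of the other, a true null is rejected in 38% of trials at a two-fold hazard difference and in 95% at a four-fold one. A reader might take these as the likely scale, but nothing in the documents supports contrasts of that size, and they should not raise the weight of the point.

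**What to change.** Keep the pooled analysis as planned. Add to section 8.6, before the outcomes are analysed:

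> The MBT Cox hazard ratio will also be reported from a model stratified by source study (HIS-EX-408, PLT-BID-1108; a patient in both belongs to the study of the last MBT), beside the pooled result. MBT distribution, events and person-years will be tabulated by study. If the two hazard ratios differ materially, the stratified one will be used for any statement about prediction among patients of the same study.

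The assignment rule is needed because the entry wording allows a patient to have been in both studies. It follows the time origin in section 3.1, which is the last MBT.

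**Cost.** One stratified model and one table. If stratifying was not needed, power of the stratified result for HR 1.30 per SD falls by about 1 to 3 points at a 0.5 SD gap. In separate runs it fell from 87.2% to 85.4% and from 85.8% to 84.4% in scenario A, and from 51.4% to 49.5% and from 49.6% to 46.6% in B. At a 1 SD gap the loss is 5 to 8 points (92.3% to 87.0% in A, 58.9% to 51.1% in B). The pooled result loses nothing.

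An MBT-by-study interaction, within-study hazard ratios and a stratified log-rank test are optional. If they are given, a non-significant interaction should not be read as consistency. As an editorial point only, section 8.1 should name both source studies, as sections 4, 5 and 8.5 do.
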